## **6.6 Weight, Height and Body Mass Index (BMI)**

Weight is measured with empty pockets and normal indoor clothes without shoes. Weight is measured at several time points according to the schedule and entered in the EDC.

Height is measured without shoes and is only measured at screening and entered in the EDC.

The BMI is calculated by the EDC.

## **6.7 Electrocardiogram (ECG)**

Equipment for recording the ECG should be recently serviced and calibrated. Machine calibration records and performance data should be maintained on file.

A standard 12-lead ECG will be obtained in supine position after at least 5 minutes at rest. A copy of the recording will be made available for the Sponsor.

At screening, any abnormalities or normal variants will be assessed for clinical relevance and recorded in the medical history. Subsequent changes will be recorded in the EDC description text field and deemed clinically relevant or not (separate files). Changes that are deemed clinically relevant are furthermore recorded as AEs.

In addition to the description above, the ECG intervals PR, QRS, RR and QT will be measured and recorded in the eCRF for QTc assessment.

## 6.8 Urine Sample Laboratory Variables

Tests on urine are conducted on a fresh midstream urine sample obtained from the participant.

### 6.8.1 Urine Pregnancy Test

All females irrespective of reproductive potential will be tested for pregnancy.

The tests at screening and end of study will be sent to the local laboratory with the sample for urinalysis described in [Section 6.8.2](#).

The test at Day -1 is performed in the CRU using a commercially available pregnancy kit and documented with a photograph. The binary negative/positive result will be recorded in the EDC. Alternatively, if the turnaround time allows, the test may be sent to the local lab.

### 6.8.2 Urinalysis

The sample for urinalysis will be sent to the local laboratory for testing.

#### 6.8.2.1 Screening

At screening, at Day -1, and at the end of study, a complete urinalysis will be done including visual inspection of color and clarity, chemical testing for specific gravity, pH, bilirubin, urobilinogen, protein, glucose, ketones, blood, leukocytes, nitrite, and creatinine.

#### 6.8.2.2 Urine PD

Participants will be instructed to empty their bladder prior to sleep. If the participant voids during the night, the urine will be collected and pooled with the first morning void. The time and volume of urine must be recorded. On Day 0 a first morning void will be collected prior to dosing, and pooled with any urine collected during the night. An aliquot will be sent for urine PD. The time on collection and total volume must be recorded.

Additional pooled urine collections will take place at the following intervals:

- Day 0: a 4-hour urine collection will begin after dosing.
- Day 0: from 4 hours post-dose until bedtime. Participants will be instructed to empty their bladders prior to sleep. If the participant voids during the night, the urine will be collected and pooled with the first morning void. The time and volume of urine must be recorded.
- Day 1 through Day 3: 12- hour urine collections.

For each collection period an aliquot of the pooled samples will be collected and tested for concentration of u-calcium, u-phosphate, u-magnesium, u-bicarbonate, u-sodium, and u-chloride and u-creatinine. The times of each void and total volume collected for each collection period must be recorded.

Participants will be provided with a 12-hr. urine collection container and instructed to collect all urine for 12 hours leading up to the out-patient visits on Days 5, 7, 14 and 28.

Results will be sent to the CRU and transferred periodically to data management.

## 6.9 Blood Sample Laboratory Variables

### 6.9.1 Blood Sample Draw

Blood is drawn either from a phlebotomy, or an indwelling catheter during the inpatient period after drawing out minimally 1 ml blood that is discarded per the investigational site's procedures.

Samples are drawn into appropriate sample container and processed according to the laboratory's instructions.

### 6.9.2 Total Amount of Blood Drawn for Sampling

The total amount drawn from screening to last visit, which is a period of time of approximately 60 days, is well under 500 ml, including potentially discarded blood from the indwelling catheter sampling procedure described in [Section 6.9.1](#).

### 6.9.3 Screening and Safety Laboratory Tests

See [Sections 7.1](#) and [7.1.1](#) for timing of lab tests.

1. Serum PTH at screening.
2. Complete blood count (CBC) including RBCs, hemoglobin, hematocrit, WBC, and platelets, at all scheduled time points.
  - a. At screening and end of study, the CBC will also include a differential count.
3. Clinical chemistry comprehensive metabolic panel including serum glucose, calcium, albumin, total protein, sodium, potassium, bicarbonate, chloride, blood urea nitrogen (BUN), creatinine, alkaline phosphatase, alanine amino transferase (ALT), aspartate aminotransferase (AST), total bilirubin.
4. Hepatitis B, C and HIV will be tested for at screening.
  - a. Hepatitis B surface antigen
  - b. Hepatitis C antibody screening test
  - c. HIV-1 and HIV-2 antigen and antibody routine screen.

Anti-Drug Antibody and Neutralizing Antibody development Lab reports will be reviewed by the investigator for clinical relevance and possible clinical laboratory adverse event reporting.

### 6.9.4 Pharmacokinetics (PK)

One 5 ml serum sample will be collected at the time points noted in [Section 7.1.1](#) and divided into 2 aliquots of 1ml each for determination of EXT608 concentrations. Samples will be shipped to the laboratory in batches, with one of the samples retained at the site in case of transfer problems.

### 6.9.5 Pharmacodynamic (PD) variables

See [Sections 7.1](#) and [7.1.1](#) for timing PD labs. Laboratory PD variables include:

See [Section 6.8.2.2](#) for urine PD variables.

## 6.10 Safety Variables and Safety Reporting

### 6.10.1 Adverse Events

#### 6.10.1.1 Adverse Events

An Adverse Event (AE) is defined as any untoward medical occurrence in a participant or clinical investigation participant administered a pharmaceutical product and which does not necessarily have to have a causal relationship with this treatment. An AE can therefore be any unfavorable and unintended sign (including an abnormal laboratory finding, for example), symptom, or disease temporally associated with the use of a medicinal product, whether or not it is considered related to the medicinal product.

Adverse events will be collected from the time informed consent is signed and until the Follow-Up or Early Termination visit.

All participants will be queried, using non-leading questions, about the occurrence of AEs at each study visit. When possible, a constellation of signs and/or symptoms should be identified as one overall event or diagnosis. All AEs for randomized subjects will be recorded in the eCRF and the subject's source documents. Adverse events for subjects who are screened but not subsequently randomized in the study will be recorded only in the subject's source documents. The following data should be documented for each AE:

- Description of the events
- Classification of “serious” or “not serious”
- Date of first occurrence and date of resolution (if applicable)
- Severity
- Causal relationship to study drug
- Action taken
- Outcome
- Concomitant medication or other treatment given

Adverse events will be rated a mild, moderate or severe intensity using the following definitions:

- Mild: “Mild” events are usually transient and do not interfere with the participant’s daily activities.
- Moderate: “Moderate” events introduce a low level of inconvenience or concern to the participant and may interfere with daily activities.
- Severe: “Severe” events interrupt the participant’s usual daily activities.

The causality will be rated in the following categories:

- Unlikely: An “unlikely” relationship suggests that only a remote connection exists between the investigational study product and the reported AE. Other conditions, including chronic illness, progression or expression of the disease state or reaction to concomitant medication, appear to explain the reported AE.
- Possible: A “possible” relationship suggests that the association of the AE with the investigational study product is unknown; however, the AE is not reasonably supported by other conditions.
- Probable: A “probable” relationship suggests that a reasonable temporal association of the AE with study product functionality exists and, in the Investigator’s clinical judgment, it is likely that a causal relationship exists between the study product’s functionality and the AE, and other conditions (concurrent illness, progression or expression of disease state or concomitant medication reactions) do not appear to explain the AE.

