### 2.1 Primary Objective

The primary objective is to characterize the safety and tolerability profile of escalating dose levels of EXT608 when administered to healthy adult participants as a single injection as assessed by:

1. Incidence, nature, and severity of adverse events (AEs) and withdrawals due to treatment emergent AEs (TEAEs) [Time Frame: Day 0 up to Day 28]
2. Frequency and severity of post-dose change from baseline in hematology, serum chemistries, urinalysis, electrocardiogram (ECG), vital signs, and physical examination (Exam) findings [Time Frame: Day 0 up to Day 28]
3. Percentage of participants with injection or infusion site reactions [Time Frame: Day 0 to Day 7]

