##### 3.1.1 Numbers of Cohorts and Participants, and Treatment Allocation

Up to approximately 30 participants may be enrolled to the study intervention such that approximately 24 evaluable participants complete the study.

Additional participants and cohorts may be enrolled pending review of study data and recommendation by a Data Monitoring Board (DMB) and ratification by the Sponsor.

Participants will be enrolled into 1 of up to 6 planned single dose cohorts (designated as S1 through S6, respectively) in ascending fashion.

Each cohort will consist of 4 participants randomized to receive either EXT608 or placebo, whereby 3 will receive a single injection of EXT608 and 1 will receive matching placebo.

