##### **4.3.1.2 Investigator determination**

The Investigator may withdraw the participant at his or her discretion should further participation for medical reasons not be in the participant's best interest, or for non-

compliance with the CRU rules and requirements. If possible, the Medical Monitor for the study should be contacted to discuss the individual case before withdrawal.

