#### **4.3.1.4 Sponsor request**

The Sponsor may request discontinuation of any participant for non-compliance with study procedures or other significant protocol violations, and may discontinue the study in the case that significant new information becomes available that renders the study unsafe or of questionable medical and scientific value to continue.

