### **4.3.3 Follow up on withdrawn participants**

Early discontinuation does not nullify the need to follow adverse events up until resolution or stabilization.

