#### **6.10.1.4 SAE Reporting Procedure**

Serious adverse events will be collected over the same time period as stated above for AEs. All SAEs must be reported regardless of the relationship to the drug. The initial report should include at least the following information:

- Subject's study ID number
- Protocol number
- Description of the event
- Criterion for categorizing the AE as serious
- Preliminary assignment of causality to study drug

Any new information should be provided as it becomes available. Copies of discharge summaries, consultant reports, autopsy reports, and any other relevant documents may also be requested.

[figure not shown]
Appropriate remedial measure should be taken by the Investigator using his/her best medical judgment to treat the SAE. These measures and the subject's response to these measures should be recorded. All SAEs, regardless of relationship to study drug, will be followed by the Investigator until satisfactory resolution or the investigator deems the SAE to be chronic or stable. Clinical, laboratory, and diagnostic measures should be employed by the Investigator as needed to adequately determine the etiology of the event.

[figure not shown]
The Investigator will be responsible for reporting all SAEs to the Institutional Review Board (IRB)/Ethics Committee (EC). The Sponsor will be responsible for reporting to the regulatory authorities.

Serious adverse events must be reported to the Sponsor within 24 hours of coming to the Investigator's attention. Any serious adverse event that occurs any time after the participant has signed the informed consent form for the study, up to the participant's final study visit, inclusive, is to be reported to Product Safety within 24 hours following when the event was first recognized, discovered, or reported, regardless of severity or relationship to the study product. If unable to enter the SAE information in the EDC (e.g., internet connection is down), the report may be reported by telephone to the Medical Monitor directly [REDACTED]

Serious adverse events must be followed up by the Investigator until resolution or stabilization.

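### AE and SAE collection ends at early termination, so new events between an early exit and Day 28 are missed although the primary measure runs to Day 28

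*Protocol*

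**What the plan says.** **Collection window.** Protocol 6.10.1.1: "Adverse events will be collected from the time informed consent is signed and until the Follow-Up or Early Termination visit". Protocol 6.10.1.4: "Serious adverse events will be collected over the same time period as stated above for AEs". The same section later gives the end of SAE reporting as the final study visit. Protocol 7.2.8 makes the early termination visit the last one, with the Day 28 assessments, and describes no later contact.

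**After withdrawal.** Protocol 4.3.3: "Early discontinuation does not nullify the need to follow adverse events up until resolution or stabilization". Section 6.10.1.2 likewise follows an AE until its outcome is known. Neither provides for finding a new event.

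**Who can end participation.** Besides the participant, the Investigator can: section 4.3.1.2 begins "The Investigator may withdraw the participant at his or her discretion should further participation for medical reasons" and adds non-compliance with unit rules as a ground. So can the Sponsor, in 4.3.1.4: "The Sponsor may request discontinuation of any participant for non-compliance with study procedures or other significant protocol violations".

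**Primary measure.** Protocol 2.1, repeated in SAP 1.2.1: "Incidence, nature, and severity of adverse events (AEs) and withdrawals due to treatment emergent AEs (TEAEs) [Time Frame: Day 0 up to Day 28".

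**Analysis.** SAP 3.1.1 defines the safety population as everyone randomized and keeps replaced participants who were dosed. SAP 3.4.5.1 reports TEAEs as numbers and percentages of participants, provided there are more than five TEAEs in the study. SAP 3.2.1 leaves missing data unestimated unless stated otherwise. No person-time or censoring method is given for AEs.

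**The concern.** In a trial of repeated dosing, leaving the study usually ends exposure as well as observation. Here the whole exposure is given on Day 0, so leaving ends observation only. The protocol itself treats the later days as informative: EXT608 is built for an extended half-life (1.2), AUC is planned to 28 days (2.2), and follow-up may be prolonged for an individual whose calcium has not settled (3.1.6).

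For anyone who leaves early, the collection window is therefore shorter than the window in which the primary measure is defined. Participants removed by the Investigator or Sponsor have not necessarily refused contact. They are the ones who could most easily still be asked about events, yet the protocol does not require it.

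At stake are late events, including SAEs, in a first-in-human trial with three active participants per dose level, and a percentage whose denominator includes a person observed for only part of the 28 days.

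**Working it through.** **The plan's own figures.** Up to 6 cohorts of 4 gives 6 × 4 = 24, which matches the approximately 24 evaluable participants in Protocol 3.1.1. Up to approximately 30 may be enrolled. The documents give no dropout rate and no figure for completeness of AE follow-up, so there is nothing further to reproduce. The exit days and risks below are assumptions.

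**Inputs from the documents**
- Active participants per cohort, Protocol 3.1.1: "whereby 3 will receive a single injection of EXT608 and 1 will receive matching placebo".
- Length of the primary measure: 28 days (Protocol 2.1).
- Person-days per dose level if all three active participants are observed throughout: 3 × 28 = 84.

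**Step 1: observation lost if one of three active participants leaves on Day t.** Unobserved share = (28 − t)/84.

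| Exit day (assumed) | Unobserved person-days | Share of 84 |
|---|---|---|
| 3 | 25 | 30% |
| 7 | 21 | 25% |
| 14 | 14 | 17% |

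**Step 2: which events can be lost.**
- *Participant withdrawn because of a TEAE.* That TEAE is recorded and followed, and the participant already counts in any-TEAE. What can be lost is a new preferred term, a new event of higher severity, or a later SAE.
- *Participant who leaves with no TEAE*, for example by choice or for non-compliance. A first TEAE after exit can be lost as well. In an arm of three, one such miss changes the reported percentage by 1/3.
- *An AE present at exit.* It is counted and followed, so nothing is lost.

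**Step 3: possible effect on a crude percentage.** Assume a true 28-day risk p, a constant hazard, and an exit unrelated to AEs. The chance of capturing an event in the leaver is 1 − (1 − p)^(t/28). The expected crude incidence in the arm is [2p + 1 − (1 − p)^(t/28)]/3.
- p = 30%, t = 7: the leaver contributes 1 − 0.7^0.25 = 0.085, and (0.6 + 0.085)/3 = 22.8%.
- p = 30%, t = 3: 21.2%. With t = 14: 25.4%.
- p = 10%, t = 7: 7.5%. p = 50%, t = 7: 38.6%.

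If events cluster soon after dosing, the shortfall is smaller; if they come late, it is larger. Uncollected events after exit can only lower the count.

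**The case against.** Several points on the other side are sound.

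- Participants are confined for at least 72 hours (Protocol 3.1.6). On withdrawal, a full end-of-study visit is made if possible, and at minimum the Investigator must judge the participant clinically stable (4.3.2).
- Participants without evaluable Day 7 data are replaced (3.3.4, 4.4), which partly protects escalation decisions. It does not repair the Day 0 to 28 measure, and an exit after Day 7 falls outside that rule.
- SAP 3.4.2 counts early terminations and SAP 3.4.5.1 lists all AEs. With so few participants, a reader could match one to the other. Even so, a count of early terminations does not show how much of the 28 days was observed, and it cannot recover an event that was never collected.
- The schedule tables, the outpatient follow-up details and the Safety Plan are not in the text available for review and could add contacts. The statements in 6.10.1.1, 6.10.1.4 and 7.2.8 are nonetheless explicit.

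A reader might infer more: that exits for medical reasons bias incidence downward at the doses that are worst tolerated. The documents do not support this. A participant withdrawn for a TEAE is already in the any-TEAE numerator, and withdrawal due to a TEAE is itself part of the primary measure ("withdrawals due to treatment emergent AEs (TEAEs) [Time Frame: Day 0 up to Day 28"). The calculation in step 3 assumes exits unrelated to AEs, so it cannot support that inference either. Nothing suggests that removals for non-compliance follow outcome.

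**Conclusion.** The concern holds in a narrow form. As written, the collection window does not deliver the Day 0 to 28 measure for a dosed participant who leaves early. That participant still enters the percentage on the same footing as one followed to Day 28. The SAP does not say this in words; it follows from the safety population and the crude percentages.

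The size depends on how many leave and when, which the documents do not predict. One Day 7 exit among three active participants would leave a quarter of that dose level's person-days unobserved. That is an illustration for one arm. A reader might scale it up by treating the difference between 30 enrolled and 24 evaluable as six early leavers. The documents do not say that this difference is dropout. Replacement is tied to missing Day 7 data, and evaluability in the per-protocol sense also excludes major violations.

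The conclusion rests on reading 4.3.3 as covering events already present, and on no further contact being specified in the material not seen. The gap is modest and cheap to close.

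**What to change.** - **Protocol 6.10.1.1 and 6.10.1.4:** state that, for every dosed participant, AEs and SAEs are collected to Day 28 regardless of early termination, by visit or telephone, unless the participant withdraws consent to contact.
- **Protocol 4.3.1.2 and 4.3.1.4:** state that withdrawal by the Investigator or Sponsor after dosing does not end safety data collection to Day 28.
- **SAP 3.4.2 or 3.4.5.1:** show, by arm, the number of participants with AE ascertainment complete to Day 28.

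The cost is protocol wording, a few telephone contacts and one table row. No participants or tests are added. Some leavers will be unreachable or will refuse, and the added row makes that visible.

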##### 3.1.4 Dose Limiting Toxicity (DLT) Criteria

A potential DLT is defined as any of the following EXT608 TEAEs that occurs during the DLT period, graded according to the NCI Common Terminology Criteria for Adverse Events (CTCAE), Version 5.0 (2):

- Grade = 3 TEAE
- Grade = 3 anemia
- Grade = 3 AST/ALT elevation; and/or
- Grade = 2 AST/ALT elevation and Grade = 2 Bilirubin elevation

- Grade = 3 QTc prolongation
- Grade = 3 Hyper- and/or Hypotension
- Grade = 2 Hyperparathyroidism
- Grade = 2 Hyperthyroidism
- Grade = 3 Hypercalcemia
- Grade = 3 Hypocalcemia
- Grade = 3 Hypophosphatemia
- Grade = 3 Hypomagnesemia
- Grade = 3 Creatinine increased

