### 3.1.5 Dose Escalation

Dose escalation decisions will be based on the NCI Common Terminology Criteria for Adverse Events (CTCAE), Version 5.0 (2) and Se-Ca levels.

The DMB will review the seven-day safety data in each cohort before authorizing the initiation of the next cohort according to the following decision tree:

1. No Grade 3 AEs suspected related to study drug and no indication of effect observed from Se-Ca will result in the next dose at 3x the previous cohort dose.
2. No Grade 3 AEs suspected related to study drug and clear indication of effect on Se-Ca will result in the next dose at 2x the previous cohort dose.
3. A Grade 3 AE suspected related to study drug in a single (n=4) cohort and the absence of prohibitive effects on Se-Ca will result in an additional cohort at the same dose.
4. A single Grade 3 AE suspected related to study drug in 2 cohorts at the same dose (n=8) cohort and the absence of prohibitive indication of effects on Se-Ca will result in a dose escalation to 1.5x the previous dose.
5. Two or more of the same Grade 3 AE within the same cohort suspected related to study drug, or average peak Se-Ca > 1.5 mg/dl above the Upper Limit of Normal (ULN) range will terminate dose escalation.
  - a. If the last dose escalation was 50% and by implication 2 cohorts received the previous dose for an n=8, the study will stop.
  - b. If the last dose escalation was >50%, the next cohort should receive a dose 2/3x the previous dose.

Any DMB recommendation that deviates from the decision tree will be ratified by the Sponsor prior to implementation.

The study schematic is presented in [Section 3.2](#).

[figure not shown]

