#### **4.3.1.3 Data Monitoring Board Recommendation**

Potential DLTs as listed in [Section 3.1.4](#) are evaluated by the DMB per the procedures outlined in the Safety Plan.

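### DLTs and escalation use CTCAE v5.0 grade, but Protocol 6.10.1.1 prescribes AE severity as mild, moderate or severe by effect on daily activities, with no CTCAE grade or mapping; an effect on escalation is possible, not shown

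*Protocol*

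**What the plan says.** **The decision scale.** Protocol 3.1.5 states: "Dose escalation decisions will be based on the NCI Common Terminology Criteria for Adverse Events (CTCAE), Version 5.0 (2) and Se-Ca levels". Each branch of its tree turns on Grade 3 AEs suspected to be related, on Se-Ca, or on both. Protocol 3.1.4 opens: "A potential DLT is defined as any of the following EXT608 TEAEs that occurs during the DLT period". It then names CTCAE v5.0 as the grading system and lists the qualifying items, among them Grade 3 QTc prolongation.

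**The recording scale.** Protocol 6.10.1.1 lists eight data items for each AE. Severity is one; a CTCAE grade is not. On severity it says: "Adverse events will be rated a mild, moderate or severe intensity using the following definitions". Of mild it says that such "events are usually transient and do not interfere with the" daily activities of the participant. Moderate and severe are defined in the same terms. The section accepts that an abnormal laboratory finding can be an AE.

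**ECG.** Protocol 6.7 says of changes after screening: "Changes that are deemed clinically relevant are furthermore recorded as AEs". It also says that "the ECG intervals PR, QRS, RR and QT will be measured and recorded in the eCRF for QTc assessment".

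**Evaluation and reporting.** Under Protocol 4.3.1.3, potential DLTs "are evaluated by the DMB per the procedures outlined in the Safety Plan". SAP 3.4.5.1 summarises TEAEs as mild, moderate and severe. SAP 3.3.3.5.2, applied to safety laboratory tests by SAP 3.3.4.4, describes laboratory severity by low, high or abnormal flags. The SAP text as read does not mention CTCAE, and its only grade is a 1-to-4 brightness scale for erythema (SAP 3.3.4.5).

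**The concern.** The escalation tree has two inputs, related Grade 3 AEs and Se-Ca. The protocol names CTCAE as the scale for the first and then prescribes a different scale for the AE record. The two scales measure different things: CTCAE can grade a laboratory or ECG finding by its value, whereas 6.10.1.1 grades by what the participant can still do that day.

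Each cohort has 3 active participants, so a single Grade 3 event is enough to change the branch. If such an event is written down as mild, or is not entered as an AE, the count depends on someone regrading it, and neither document assigns that task. The final severity tables would also be on a scale other than the one that drove dosing, in a trial whose primary objective is safety and tolerability.

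**Working it through.** The plan gives no figure to reproduce. The check compares the sections and then sizes the worst case.

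**1. Where recorded severity can diverge from CTCAE grade**
- *Laboratory AE.* It is graded by CTCAE in 3.1.4 and by daily activities in 6.10.1.1. A transient, symptom-free abnormal value fits the mild definition whatever its size. The SAP flags show that a value is outside range, not by how much. The numeric result is kept (SAP 3.4.5.2 lists all safety laboratory results).
- *Symptom-based AE.* The first item in 3.1.4 covers any Grade 3 TEAE. No measured value exists from which to rebuild the grade, so the recorded intensity may be the only severity data.
- *QTc.* Under 6.7 a change is entered as an AE if deemed clinically relevant. Under 3.1.4 a potential DLT must be a TEAE. Read together, a Grade 3 QTc change not deemed relevant falls outside the DLT definition. The intervals are still in the eCRF.

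**2. How many listed items are involved**
- Items in 3.1.4: 13.
- Grade 3 laboratory or ECG items: anemia, AST/ALT, QTc, hypercalcemia, hypocalcemia, hypophosphatemia, hypomagnesemia, creatinine = 8.
- Less the two calcium items, which partly reach the tree through Se-Ca: 8 − 2 = 6, made up of 5 laboratory items and 1 ECG item.
- The AST/ALT-with-bilirubin item is Grade 2. The tree counts Grade 3, so it is left out.
- Of the 5 laboratory items, phosphate, magnesium and creatinine are named PD variables (Protocol 2.2, SAP 3.3.3.5), and DMB packages include PK/PD data (Protocol 8.3). That leaves anemia and AST/ALT (5 − 3 = 2), which are covered by the safety data the DMB reviews.

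**3. Worst-case dose consequence.** Suppose one related Grade 3 event in a cohort, no other Grade 3 AE, and Se-Ca not prohibitive.
- Counted: branch 3 applies, which "will result in an additional cohort at the same dose" (1x). If the repeat cohort has none, branch 4 raises the dose to 1.5x.
- Not counted: branch 2 gives 2x, or branch 1 gives 3x.
- Ratio for the next cohort: 2/1 = 2 to 3/1 = 3.
- Ratio for the next higher dose level: 2/1.5 = 1.33 to 3/1.5 = 2.

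**4. Sensitivity, under assumed inputs only.** Let p be the chance of a related Grade 3 event per active participant, independent between participants, and s the chance that such an event is counted as Grade 3. Neither is in the documents. With 3 active participants, P(at least one counted) = 1 − (1 − ps)³.

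| p | s = 1 | s = 0.5 |
|---|---|---|
| 0.1 | 0.271 | 0.143 |
| 0.2 | 0.488 | 0.271 |
| 0.5 | 0.875 | 0.578 |

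This shows the direction of the effect and how a small cohort responds to under-counting. It is not evidence that s is below 1.

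**The case against.** The strongest reply is that the decision scale is stated. Sections 3.1.4 and 3.1.5 name CTCAE v5.0, and nothing says that the tree reads the 6.10.1.1 severity field, so a mild entry does not prevent a Grade 3 call. The people able to make that call see the data:
- The Investigator(s) and Medical Monitor are voting DMB members (7.3.1) and carry out the 72-hour sentinel review (3.1.3).
- No outcomes are blinded (5.4.2).
- The DMB receives a cohort data summary (7.3.2) covering safety and PK/PD (8.3).
- It may depart from the tree with Sponsor ratification (3.1.5).

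The documents reproduce no CTCAE thresholds, so the six items are a count of labels. It is not shown that each can reach Grade 3 without symptoms. The QTc route requires an investigator to judge a protocol-listed DLT criterion not clinically relevant. The Safety Plan and eCRF are unavailable, and some protocol content is not shown.

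Most of this stands, and it rules out three stronger readings. A reader might infer that Grade 3 events will be missed and doses raised wrongly. The documents do not support that, because raw values are kept and the DMB sees cohort data. A reader might infer that the final tables can never be reconciled with the escalation decisions. That goes too far, because AEs, laboratory results and ECG values are all listed and value-based grades could be rebuilt. A reader might extend the ECG relevance condition to all laboratory values from the last sentence of 6.9.3. As it reads, that sentence concerns antibody reports, so the point does not rest on it.

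The reply does not remove the conflict between 3.1.4/3.1.5 and 6.10.1.1. Regrading is assigned to nobody in the text as read, and SAP 3.5 limits interim summaries to selected variables defined in another plan. Symptom-based events have no value to regrade from.

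**Conclusion.** The point holds as an inconsistency in the text: the scale prescribed for AE severity is not the one that the trial's own decision rule needs. The 6.7 condition adds one route by which a listed QTc finding could stay outside the DLT definition.

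Its effect on escalation is possible, not demonstrated. The 2- to 3-fold difference in the next cohort's dose is a worst case. It assumes that a related Grade 3 event goes uncounted by the Investigator, the Medical Monitor and the rest of the DMB. The documents give no frequency for such events or for failures to regrade, and the Safety Plan may already contain a grading step. Final severity tables would not be on the escalation scale, though value-based grades could be recovered from listings. This is a cheap improvement that is worth making. It does not show that escalation was unsafe.

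**What to change.** 1. In Protocol 6.10.1.1, record the CTCAE v5.0 grade for every AE, in place of or alongside the present three levels. Take it from the measured value where CTCAE grades by value. Summarise TEAEs by that grade in SAP 3.4.5.1.
2. In Protocol 3.1.4 and 6.7, state that any post-dose laboratory or ECG value at a listed grade goes to the DMB as a potential DLT whatever the relevance call, and is entered as an AE if the DMB counts it.

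The cost is one eCRF field and short edits to those four sections, with no extra sample or visit. The downside is that sites must grade by CTCAE and the DMB will spend some time on transient, symptom-free values. If the Safety Plan already grades this way, the edits only bring the protocol and SAP into line with it.
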